Due to poor recruitment levels with our original study design, we are requesting a revision of the protocol to reflect updated study procedures. As of 9/28/17- we have enrolled one patient in the study who has completed all study procedures. The data for this 1 participant will be analyzed, but not included in the total n for STUDY 2. This participant has completed all study procedures and will not be informed directly that the study 1 has been modified to STUDY 2, as the modification was not due to concern of risk to subjects, rather that a sufficient number of subjects in our local community did not meet eligibility criteria..

Our revised protocol (named STUDY 2), instead of focusing on both naturalistic dual use behaviors and behaviors while switching to e-cigarettes, now is focusing only on the naturalistic behaviors of 32non-treatment seeking young adult e-cigarette/combustible tobacco product dual users. Combustible tobacco products include **cigarettes, cigars, cigarillos, hookah, roll your own cigarettes**).

In this one-year pilot study of 32 non-treatment seeking young adult e-cigarette/combustible tobacco product dual users (16 males/16 females), we will use smartphone-based ecological momentary assessment (EMA) to gather real-time data of e-cigarette and combustible tobacco product behaviors during a naturalistic 1-week combustible tobacco product/e-cigarette dual use period. (1) Participants will respond to daily random prompts assessing in-the-moment use of e-cigarettes/cigarettes and the subjective factors (ratings of satisfaction and withdrawal) and contextual factors (location, activity, social cues) associated with each episode of use. They will also complete daily electronic diaries to document e-cigarette use episodes/day, amount of e-liquid used, cigarettes smoked/day, nicotine concentrations and flavors used during the day, and how satisfied they were with the e-cigarette experience during the study. They will be queried about whether they changed product constituents (flavors, numbers of flavors, nicotine concentrations). We will also collect markers of carbon monoxide and nicotine exposure (CO, cotinine) throughout the study.

STUDY 2

Aim 1: To determine how within-subject's ratings of subjective factors (withdrawal, satisfaction with tobacco products) change between episodes of e-cigarette use vs. episodes of other combustible tobacco product use (cigarettes, cigars, cigarillos and/or hookah).

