Hypothesis A: Young adult dual users, particularly males, will report lower satisfaction and higher withdrawal scores with episodes of e-cigarette use, in comparison to episodes of combustible tobacco product.

Aim 2: To examine gender differences in e-cigarette use patterns among young adult dual users.

Aim 3: To examine gender differences in e-cigarette use patterns among young adult dual users.

Hypothesis B: Young men will be more likely smoke/vape for the rewarding effects of nicotine.

Hypothesis C: Young women will be more likely to smoke/vape in response to contextual reasons.

Exploratory Aim: To examine sex differences in within-subjects' changes in cotinine levels during the dual use periods.

STUDY 2

2. Research Plan:

- a. **Overview:** In this one-year pilot study of 32 non-treatment seeking young adult e-cig/combustible tobacco product dual users (15 males/15 females), we will use smartphone-based ecological momentary assessment (EMA) to gather real-time data of e-cigarette and combustible tobacco product behaviors during a 1-week cig/e-cigarette dual use period. Participants will be eligible if they self-report use of e-cigarettes at least one day during the past 7 days and use of at least one other combustible tobacco product at least one day during the past 7 days. Participants will respond to daily random prompts assessing in-the-moment use of e-cigs/combustible tobacco products and the **subjective factors** (ratings of satisfaction and withdrawal) and **contextual factors** (location, activity, social cues) associated with each episode of use. They will also complete daily electronic diaries to document e-cigarette use episodes/day, amount of e-liquid used, combustible tobacco products smoked/day, nicotine concentrations and flavors used during the day, and how satisfied they were with the e-cigarette experience during the study. They will also be queried about whether they changed product constituents (flavors, numbers of flavors, nicotine concentrations). We will also collect markers of carbon monoxide and nicotine exposure (CO, cotinine) throughout the study.

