Study visit *	Baseline study visit (\$15)		a						F/U visit (\$15) and payment for EMA	\$30
Remuneration for EMA		Participant completed smart-phone based Ecological Momentary Assessments								\$50
85% EMA completion incentive										\$14
CO breath test: On-time/valid sample, regardless of the CO value (split for am/pm payment)		\$2 (\$1/\$1)	\$4 (\$2/\$2)	\$6 (\$3/\$3)	\$8 (\$4/\$4)	\$10 (\$5/\$5)	\$12 (\$6/\$6)	\$14 (\$7/\$7)		\$56
*Study visit activities: a) Review EMA procedures via phone									TOTAL:	\$150

Length of Study Visits

Baseline: 1.5 hours

STUDY 2 Follow-Up (Day 8-10): Up to 30 minutes

e. **Primary Outcome:** The primary outcomes are daily mean withdrawal scores (measured 3x/day with the Mood and Physical Symptoms Scale) and satisfaction with e-cigarette (measured daily with a 1-10 Likert scale).(65)

STUDY 2

f. **Baseline assessments Demographics:** age, gender, race, ethnicity, and level of schooling completed. **Combustible Tobacco Product Smoking:** Structured Timeline Follow-Back (TLFB) interviews will document the # of combustible tobacco products smoked per day during the past 28 days.(66) **E-Cigarette Use:** Structured TLFB interviews will document the # of episodes of e-cigarette use per day during the past 28 days. We will also query participants about nicotine concentrations used, flavors used, and the mls of liquid used/day. We already have extensive experience with the collection of these measures from work with adolescent e-cigarette users in the Yale TCORS project. **Nicotine Dependence:** Fagerstrom Test of Nicotine Dependence-R, a 6-item scale to estimate the severity of dependence.(67) **Abstinence Self-Efficacy:** The Smoking Self Efficacy Questionnaire to measure self-efficacy.(68) **Preferred Product Features:** Participants will be asked to bring their preferred cigarette and e-cigarette to the baseline visit. We will record the brand/type of cigarette and e-cigarette (brand, nicotine concentration, flavor, battery voltage, tank/cartridge size, propylene glycol/vegetable glycerin ratio).

STUDY 2

g. **Time based and Event based sampling procedure (EMA):**

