Daily Momentary Assessments: Participants will be randomly prompted with the MetricWire app up to 3x daily to provide data on e-cigarette/combustible tobacco product use in the last 15 minutes, the type of e-cigarette/combustible tobacco product used (brand/type), subjective factors (withdrawal) and the contextual factors surrounding the episode. **Subjective factors** will include *Mood* and *Withdrawal*. To maintain brevity during the random prompts, We will use the Mood and Physical Symptoms Scale (MPSS) to measure severity of five withdrawal symptoms (depressed, irritable, restless, hungry and poor concentration) and urge to smoke (craving).(65) Total score ranges from 5 to 25 with a higher score indicating a higher severity of withdrawal symptoms, we will use the International Positive and Negative Affect Schedule Short Form's measures of negative affect.(69) Participants will rate on a 5 point scale their agreement with experiencing the following emotion: (upset, hostile, ashamed, nervous, afraid). **Contextual factors** will include questions about *Companionship* (“During this smoking/vaping episode, who were you around?”) (smoker, person who is vaping, non-smoker, alone)), *Location* (“Where were you?”) (home, work/school, vehicle, bar/restaurant/store, other)), and *Activity* (“What were you doing?”) (eating/drinking a non-alcoholic beverage, drinking alcohol, working/reading/studying, traveling, socializing, other)). Participants will have 30 minutes to respond to random prompts; otherwise data will be considered lost. Each random prompt will be date- and time-stamped and record whether the assessment was completed, missed, delayed, or disbanded. *This method aims to accrue a representative sample of occasions focused on the participants' immediate state.*

STUDY 2

Daily Electronic (e-) Diaries: Participants will fill in daily night-time e- diaries via the app to provide data on e-cigarette use (episodes of e-cigarette use/ day) and combustible tobacco product smoking (# combustible tobacco products smoked/day). They will provide a rating of satisfaction with the e-cigarette they used during the day, and overall satisfaction rating of using their e-cigarette (1-10 Likert scales). Participants will record pictures of the e-cigarette(s) used during that day via the MetricWire app and provide a description of features. *We have chosen daily night-time e-diaries to minimize participant burden.*

STUDY 2

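### The companionship item presupposes use, and no use-versus-no-use analysis is planned, so Hypothesis C cannot separate response to context from time spent in it

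*Combined protocol and SAP*

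**What the plan says.** Hypothesis C reads "Young women will be more likely to smoke/vape in response to contextual reasons". The opening description of Study 2 and section 2.a both say that momentary data will cover context ("location, activity, social cues) associated with each episode of use").

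Section 2.g (Daily Momentary Assessments) sets up to three random prompts a day. Each asks about product use in the preceding 15 minutes, about withdrawal, and about "the contextual factors surrounding the episode". Three context items follow:

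- Companionship is worded "During this smoking/vaping episode, who were you around".
- Location and activity ask where the participant was and what they were doing, without naming an episode.

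The same section says that the method "aims to accrue a representative sample of occasions".

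In Statistical Consideration (item 11), the Analysis Plan compares e-cigarette episodes with combustible episodes for Aim 1. For Aim 2 it compares the sexes on e-cigarette use patterns and says that change in contextual factors will be evaluated. It does not mention Hypothesis C or a comparison of use moments with no-use moments. The Overview of item 11 names logistic mixed models for binary data.

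**The concern.** To say that someone uses in response to a setting, one must know how often they are in that setting without using. If only use moments carry context, the analyst sees the share of episodes in each setting. That share depends both on time spent there and on how much more likely use is there.

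If women spend more of their day with other people than men do, more of their episodes will occur in company even when company has no bearing on use, and Hypothesis C will look confirmed. If women spend less time in company, a real difference in responsiveness can disappear. More participants would not help, because the interval would narrow around the wrong quantity.

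Nothing listed in the baseline assessments (2.f) or the nightly diaries (2.g) records time spent in each setting, and no-use contexts cannot be recovered once the week is over. The pilot's estimates are meant to inform later studies, so a confounded estimate would be carried forward.

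**Working it through.** **The plan's own figures.** None concerns Hypothesis C. The sample size section gives a 95% CI of 0.37 SD for a mean change with 30 subjects. This reproduces as t(0.975, 29)/√30 = 0.373 and has no bearing here.

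**Identification.** Let p be the share of time in a context, and r1 and r0 the probability of use in and out of it. Among use moments, the odds of being in the context are [p/(1−p)] × (r1/r0). The female-to-male odds ratio is therefore

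use-only OR = {[pW/(1−pW)] / [pM/(1−pM)]} × {(r1/r0 in women) / (r1/r0 in men)}.

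Use-only data give the product. Hypothesis C concerns the second factor.

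**Numbers (exposure shares are assumed; the documents give none).**

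| Women v men, share of time with others | Ratio of relative use rates | Use-only OR |
|---|---|---|
| 60% v 40% | 1.0 | 1.5/0.667 = 2.25 |
| 55% v 45% | 1.0 | 1.222/0.818 = 1.49 |
| equal | 1.0 | 1.0 |
| 40% v 60% | 2.25 | 0.444 × 2.25 = 1.0 |

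A second illustration uses men who spend 30% of their time in a context that does not affect use, so 30% of their episodes fall in it. Women with 50% of time there and use probability 0.20 in and out show 50%. Women with 30% of time there and use probabilities of 0.35 and 0.15 (odds ratio 3.05) also show 0.105/(0.105 + 0.105) = 50%. The gap of 50% v 30% is the same, with opposite explanations.

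**Amount of data.** Prompts number at most 32 × 7 × 3 = 672. At 85% answered (the incentive threshold in Table 1, used as an assumption) this is 571. With e episodes a day of each product over 16 waking hours (assumed), the share of prompts showing use is 2 × e × 0.25/16. For e = 1, 3 and 10 this is about 3%, 9% and 31%. At one episode of each product a week, which eligibility allows, it is 0.45%, or about 3 of 571 prompts.

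**Simulation at this size.** Settings: 16 women and 16 men, 21 prompts each, 85% answered, person-level SDs of 0.5 (context) and 0.7 (use) on the logit scale, 2,000 runs per setting, random-intercept logistic models. The SDs are assumed.

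| | 3% use (17 prompts) | 10% (57) | 30% (171) |
|---|---|---|---|
| Use-only, no context effect, 60/40: 95% CI excludes 1 | 6% | 27% | 64% |
| Use-only, no context effect, 55/45 | 2% | 10% | 23% |
| Use-only, no context effect, equal time | 2% | 4% | 5% |
| Use v no-use model: 95% CI is estimate × or ÷ | about 10 | 3.4 | 2.2 |
| Use v no-use model, true ratio 2.25, exposure 40/60: median | 2.29 | 2.18 | 2.24 |
| Same runs: 95% CI excludes 1 | 10% | 23% | 49% |

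At 3% use, 19% to 23% of use-only fits could not be estimated and were dropped. With no context effect, the use v no-use model gave median ratios of 0.96 to 1.04 and coverage of 95% to 97%. With SDs halved or doubled, or 60% answered, its CI factors ranged over 9.6 to 18, 3.3 to 4.5 and 2.2 to 2.7.

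**The case against.** **Only one item is shown to presuppose use.** This stands. A reader might infer that all three context items are confined to use episodes. The documents do not support that. Location and activity name no episode, and the app's skip logic is not in the documents. The phrase tying these factors to each episode of use also covers withdrawal, which section 2.e measures three times a day with no use condition, so it cannot be read as a skip rule.

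**The sampling is already representative.** The stated intent describes when prompts fire, not which items appear after a report of no use. It helps the remedy, because the schedule already reaches no-use moments. The heading of 2.g also mentions event-based sampling, but no event procedure is described, and reports of use events would again be use moments.

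**Hypothesis C is loosely worded and not tied to the primary outcomes.** This is fair, and it limits the importance of the point. A description of episode contexts by sex serves the aim on use patterns. If the hypothesis instead means self-reported reasons, none of the listed items asks for reasons.

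**The sizes are assumed, and the remedy is imprecise.** Both parts stand. The 64% figure needs a 20-point exposure gap and use at 30% of prompts, roughly ten episodes a day of each product. At 3% use, false signals are rare, but the recommended model is then nearly uninformative too.

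**The remedy shows association only.** This also stands. Use and context share one 15-minute window, so someone may seek company, or solitude, because they are about to use.

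**Conclusion.** The point holds for Hypothesis C. The companionship item cannot supply no-use contexts, the position for location and activity is unstated, and no planned analysis would use such data. A sex difference in episode contexts is therefore not evidence of a sex difference in response to context. With no context effect, the use-only odds ratio could be 2.25, 1.49 or 1.0, depending on assumed exposure shares of 60/40, 55/45 or equal.

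Two stronger conclusions might be drawn, and neither is supported. The documents do not show that the result will be biased, since with equal exposure there is no distortion. Nor is the study as a whole undermined: the primary outcomes (withdrawal and satisfaction), the description of episode contexts by sex, and the comparison of e-cigarette with combustible episodes are unaffected. This is an inexpensive improvement to one pilot hypothesis, worth making before data collection.

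**What to change.** 1. Reword companionship to ask whom the participant was around in the preceding 15 minutes, and ask it at every answered random prompt, whether or not use is reported. State that location and activity are asked at every prompt too, with the same window.
2. For Hypothesis C, prespecify one binary context (for example alone v not alone) and fit a logistic mixed model of use v no use with a random subject intercept. Include sex, the within-person deviation in context, the person mean of context, and sex × within-person deviation. Report the exponentiated interaction (a ratio of odds ratios) with its 95% CI as a pilot estimate of association. State that use and context share one window, so the order of events is unknown.
3. Prespecify a minimum number of use prompts below which only descriptions are given. As a guide, 57 gave a CI factor of about 3.4, and 17 about 10.
4. If the items cannot be changed, restate Hypothesis C as a description of contexts of use by sex.

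**Cost.** At 10% use there are about 571 × 0.9/32 = 16 no-use prompts per person, so up to 16 × 3 = 48 extra short answers in the week (about 7 a day). If location and activity are already asked there, it is 16. This works against the stated aim ("To maintain brevity during the random prompts"). The link between context and episode becomes slightly looser if company or place changes within the 15 minutes. No extra prompts, staff or participants are needed. Intervals will be wide, and if use is rare the pilot cannot answer Hypothesis C even with the change.

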Participant Training upon Study Enrollment: The RA will teach participants to use the smartphone-based EMA data collection tool and to follow CM procedures. Participants will be instructed to: (1) continue smoking combustible tobacco products ad libitum without changing their smoking frequency/pattern during the study; (2) provide and use their own combustible tobacco products and e-cigarette and liquid during the study. The subjects will be paid for the week of EMA participation and CM-reinforced CO monitor video submissions at the follow-up appointment.

EMA data collection tool: We will use the MetricWire Android and iOS mobile applications (“apps”) for EMA data collection.(64) Participants will submit responses to survey questions and upload multimedia via the app. With guidance from the Canadian and U.S. Governments, the app is designed in careful reference to Good Clinical Practice (GCP), including the FDA’s part 11 HIPAA regulatory compliance. The app generates random prompts with the ability to set minimal interval time between prompts. Participants will also be prompted to complete daily night-time diaries. **5.1. Quality Checks and Procedures:** Data will be stored on a HIPAA and 21 CFR Part 11 compliant servers and encrypted during transit. Study investigators will have access through an encrypted web-based application. Participant data is uploaded from the mobile app when it is connected to wireless. The RA will check the database daily to complete and correct data entry.

STUDY 2

Contingency management (CM) procedure: On days 1-7, the MetricWire app will randomly prompt participants twice daily (in am and pm) to record a video of them blowing into the CO monitor. They will text/email (via their phone) the video to the study phone/e-mail. To promote video documentation, participants will receive \$1 for each on-time, valid video submission; this will continue to increase by \$1 per valid video submission for each consecutive daily video submission up to a maximum of \$14/day on Day 7 per Table 1. There will be a reset contingency for lack of video submission; participant’s payments will be reset to the initial (\$2.00/day) amount. The total possible CM payment is \$56, and total possible compensation for study participation is \$150 (Table 1).

UPDATED Table 1: Study 2 Study Flow and Contingency Management Reinforcement Schedule

WEEK 1	Day 0	1	2	3	4	5	6	7	DAY 8-10	TOTALS

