a. Justification of Sample Size: Estimation of sample size (n=32) is based on achieving a clinically meaningful precision in effect size estimates for the primary outcome of interest. With 30 subjects we will be able to construct a 95% CI for the mean change in e-cigarette episodes/day from week 1 to 2 of width up to 0.37 standard deviations away from the mean (Aim 1) and 95% CI for the slopes of the regression relationships in Aim 2 of half-widths up to approximately 0.67 of the corresponding slope values. The obtained interval estimates will be used to inform future larger definitive studies.

Analysis Plan: Aim 1 will determine how within-subject's ratings of subjective factors (withdrawal, satisfaction with tobacco products) change between episodes of e-cigarette use vs. episodes of other combustible tobacco product use (cigarettes, cigars, cigarillos and/or hookah)

During e-cigarette and combustible tobacco product use periods. We will evaluate the variability in levels of satisfaction and withdrawal scores during these periods. Correlations between repeated measures on an individual will be modeled with random subject effects. Aim 2 will evaluate gender differences in e-cigarette use patterns among young adult dual users mean changes in e-cigarette use between the dual use and exclusive e-cigarette use period that differ by sex. We will evaluate changes in contextual factors and will assess effect sizes and construct 95% CIs for change in e-cigarette use

12. Data Management:

Quantitative outcomes will be collected using paper forms which will be double entered into a secure database. Error checking and data validation will occur weekly and any problems will be queried and resolved immediately. [name] will create monthly data quality reports to check for completeness and accuracy of key variables, as well as rates of recruitment, retention, and follow-up. Baseline demographics and smoking behaviors will be summarized. Continuous data will be expressed as mean values with standard deviations and categorical data will be presented as counts with percentages.

SECTION VII: RECRUITMENT/CONSENT AND ASSENT PROCEDURES

1. Targeted Enrollment: Give the number of subjects:

- a. targeted for enrollment at Yale for this protocol_32
- b. If this is a multi-site study, give the total number of subjects targeted across all sites _____

2. Indicate recruitment methods below. Attach copies of any recruitment materials that will be used.

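### The Aim 2 analysis text names a contrast with an exclusive e-cigarette period that Study 2 does not have, and specifies no outcome or sex contrast within the single dual use week

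*Combined protocol and SAP*

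**What the plan says.** The Study 2 revision text says that the study, "instead of focusing on both naturalistic dual use behaviors and behaviors while switching to e-cigarettes, now is focusing only on the naturalistic behaviors". Data are gathered "during a naturalistic 1-week combustible tobacco product/e-cigarette dual use period". Under Participant Training upon Study Enrollment, participants are told to "continue smoking combustible tobacco products ad libitum without changing their smoking frequency/pattern during the study". Table 1 has a baseline visit on Day 0, assessments on Days 1 to 7 and a follow-up visit on Day 8-10.

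The aims list gives "Aim 2: To examine gender differences in e-cigarette use patterns among young adult dual users". In item 11 the Aim 2 sentence of the Analysis Plan opens in nearly the same terms, "Aim 2 will evaluate gender differences in e-cigarette use patterns among young adult dual users". With no joining word it then runs on to "mean changes in e-cigarette use between the dual use and exclusive e-cigarette use period that differ by sex". The paragraph closes by promising to evaluate changes in contextual factors and to give 95% CIs for change in e-cigarette use.

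The Overview of item 11 supplies a general framework: linear mixed models where normality is reasonable, logistic mixed models for binary data, negative binomial or Poisson mixed models for counts, and an effect size with 95% CI for every aim.

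**The concern.** A change between two periods needs two periods, and the second one named in the Aim 2 text is not in the Study 2 schedule. The aim itself asks whether men and women differ in how they use e-cigarettes. That is a between-sex comparison of levels within one week, not a change across periods.

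Item 11 promises an effect size with a 95% CI for each aim, to inform future studies. The one contrast written out for Aim 2 cannot supply it, and an analyst would have to choose the outcome, the sex term and the scale after seeing the data. Readers planning a larger study would also have only the precision figures in the sample-size paragraph, and neither describes a sex comparison within the dual use week.

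**Working it through.** **Can the stated contrast be formed?**

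- Periods required by the Aim 2 text: a dual use period and an exclusive e-cigarette period.
- Periods scheduled in Table 1: one dual use week (Days 1-7). Exclusive e-cigarette periods: 0.
- Instruction to participants: combustible use continues unchanged throughout.

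The contrast is therefore available for 0 of 32 participants. Days on which someone happens not to smoke would be self-selected, and the plan does not define them as a period.

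**Do data exist for the current Aim 2 question?**

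- Nightly diaries record e-cigarette episodes per day: at most 32 × 7 = 224 person-days, or 30 × 7 = 210 with 15 per sex. Both assume complete diaries.
- Random prompts, up to three a day, record companionship, location and activity: at most 32 × 7 × 3 = 672 prompts. Only those that report recent use contribute an episode.
- A 28-day Timeline Follow-Back at baseline describes prior e-cigarette use.

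The data are there. What is missing is a named outcome, a sex term and a contrast.

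**What precision does the plan state, and for what?**

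The sample-size paragraph gives two figures for 30 subjects.

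1. A 95% CI half-width of 0.37 SD for mean change in e-cigarette episodes per day from week 1 to week 2 (labelled Aim 1). For a one-sample mean change the half-width in SD units is t(0.975, n−1)/√n. With n = 30 it is 0.373, which reproduces the plan. With n = 32 it is 0.361.
2. A half-width of about 0.67 of the slope for regressions in Aim 2. The relative half-width is t(0.975, n−2) × √((1−r²)/(n−2))/r. With n = 30 and r = 0.50 it is 0.670, which also reproduces the plan, but the documents do not state the correlation. At n = 30 it runs from 0.89 (r = 0.4) to 0.52 (r = 0.6). The Analysis Plan names no regression for Aim 2 to which this figure would apply.

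**What precision does a sex comparison have?**

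For the difference between two groups of m in a person-level weekly summary, the half-width in SD units is t(0.975, 2m−2) × √(2/m).

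| Per sex | Source of the split | Half-width |
|---|---|---|
| 16 | Study 2 revision text | 0.722 SD |
| 15 | Research Plan overview; Subject Population | 0.748 SD |

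Against 0.373 these are 0.722/0.373 = 1.94 and 0.748/0.373 = 2.01 times as wide. The SDs are of different quantities: within-person change in the first case, spread between persons in the second. The comparison is of standardised precision only.

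**The case against.** Four arguments on the other side deserve weight.

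- **The clause may already have been deleted.** The sentence runs together two constructions with no joining word, and Recruitment and Screening shows two sample sizes side by side (30 and 32). Both fit a tracked revision whose strikethrough was lost when the PDF was read. This is plausible and cannot be settled from the text. If it is so, the impossible contrast disappears, but what remains restates the aim and still has no outcome or contrast.
- **The plan is not silent on Aim 2.** A reader might infer that the current question has no analysis at all. The documents do not support that: the sentence opens with the current question, and the Overview supplies model families by data type and a 95% CI for each aim. What is missing is the specification.
- **Change need not mean change between periods.** Aim 1 uses the word for differences between episodes within a person, and contextual factors are recorded several times a day. Within-week variation can be estimated. Striking the contextual phrase without replacement would remove the only analysis text for the data behind Hypothesis C.
- **Mislabelling is not planned.** A reader might infer that some substitute change, such as early against late days or baseline recall against the diary week, would be reported as a response to switching. Item 11 plans no such contrast. The Potential Benefits section does still speak of learning how young people switch, but that shows uneven revision, not an intended analysis.

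All four stand. None makes the dual-versus-exclusive contrast estimable under Study 2.

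**Conclusion.** The point holds in a limited form. As the text stands, the written Aim 2 contrast requires an exclusive e-cigarette period that Study 2 does not schedule, and no outcome or sex contrast within the dual use week is specified for the aim as now stated. The first part depends on the clause being live text; the second holds either way.

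A sex comparison of a weekly summary has a 95% CI half-width of about 0.72 to 0.75 SD, roughly twice the 0.37 SD given for a one-sample change. These figures assume equal group sizes, a common SD, an approximately normal person-level summary and complete follow-up. The documents give no SD, so the half-width cannot be turned into episodes per day or a rate ratio.

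The importance is moderate. The Primary Outcome section names withdrawal scores and satisfaction, which Aim 2 does not address, and the study is an observational pilot. It should be corrected before analysis, but it does not put the study's main results in doubt.

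**What to change.** In the Analysis Plan of item 11:

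1. Remove the dual-versus-exclusive clause and the closing reference to change in e-cigarette use, or confirm that they were already deleted.
2. State the Aim 2 estimand as the male/female rate ratio with 95% CI for diary e-cigarette episodes per day over days 1-7. Estimate it from a count mixed model with sex as a fixed effect and a random subject effect, negative binomial or Poisson according to dispersion, as the Overview allows.
3. Replace the phrase on changes in contextual factors with sex differences in the contextual factors of use episodes recorded at the random prompts. Use a logistic mixed model with a random subject effect, with each context coded as a binary indicator, so that Hypothesis C keeps an analysis.
4. State the precision of the between-sex comparison (about 0.72 SD with 16 per sex, 0.75 SD with 15), and reconcile the total of 32 with the 15/15 split, which sums to 30.

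The cost is wording only, since the diary and prompt data are already planned. The drawback is that the stated precision becomes visibly less favourable.
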